7.9.2 Laboratory Results

The observed value and change from baseline to the end of reporting period for serum chemistry, hematology and urinalysis will be summarized by dose group. The shift in observed value with

respect to normal range between baseline and end of reporting period will also be summarized for serum chemistry, hematology, and urinalysis data.

By-subject listings of laboratory results (serum chemistry, hematology, and urinalysis) will be provided for baseline and the end of the reporting period. Listings will also be provided for clinically significant laboratory values at any time post-baseline that were not considered clinically significant at Baseline.

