5.2 Primary Endpoints

The primary endpoints of this study were related to the long-term safety of intrathecal HGT-1410 administration. The safety endpoints were:

[figure not shown]
- AEs (type and severity)
- changes in clinical laboratory testing (serum chemistry including liver function tests, hematology, and urinalysis)
- electrocardiograms (ECG)
- CSF chemistries (including cell counts and inflammatory markers)
- anti-rhHNS antibodies (in CSF and serum).

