5.4 SOPH-A-PORT Mini S Assessments

6 STATISTICAL ANALYSIS

6.1 General Methodology

All statistical analyses will be performed using SAS[®] Version 9.3 or later.

Tabular summaries will be presented by rhHNS dose group (10, 45, and 90 mg). Continuous variables will be summarized using descriptive statistics [sample size (N), mean, standard deviation (SD), minimum, median, and maximum]. Categorical variables will be summarized using the number and percentage in each category. Graphical techniques will also be used to assess trends across time per treatment group. In particular, spaghetti plots to help visualize the trajectories or time trends of individual subjects within the same plot will be used. For all analyses, baseline will be the measurement from the day the subject received their first IT dose of HGT-1410 in Study HGT SAN 055. Results (e.g., mean, SD) from all visits will be displayed with significant digits consistent with the measured precision of the test or original value.

For samples associated with multiple tests performed at the same visit (e.g. lab results), the latest valid result will be selected for analysis.

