7.9.3 CSF Standard Chemistries

The CSF standard chemistries will be analyzed in a manner similar to that described in Section 7.9.2.

A by-subject listing of CSF standard chemistries at baseline and the end of the reporting period will be provided. Clinically significant CSF laboratory values at any time post-baseline that were not considered clinically significant at Baseline will also be listed by subject.

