10.3.1.7:	Summary of Investigational Product Related Treatment Emergent Adverse Events I by System Organ Class, Preferred Term, and rhHNS Dose Group – Safety Population

Table	Table Title
10.3.1.8:	Serious Treatment Emergent Adverse Events by System Organ Class, Preferred Term, and rhHNS Dose Group– Safety Population
10.3.1.9:	Treatment Emergent Adverse Events Leading to Discontinuation by System Organ Class, Preferred Term, and rhHNS Dose Group – Safety Population
10.3.2.1:	Serum Chemistry Laboratory Values: Observed and Change from Baseline to End of Reporting Period by rhHNS Dose Group – Safety Population
10.3.2.2:	Hematology Laboratory Values: Observed and Change from Baseline to End of Reporting Period by rhHNS Dose Group – Safety Population
10.3.2.3:	Urinalysis Laboratory Values: Observed and Change from Baseline to End of Reporting Period by rhHNS Dose Group – Safety Population
10.3.2.4:	Cerebrospinal Fluid Values: Observed and Change from Baseline to End of Reporting Period by rhHNS Dose Group – Safety Population
10.3.2.5:	Serum Chemistry Laboratory Values: Shift from Baseline to End of Reporting Period by rhHNS Dose Group – Safety Population
10.3.2.6:	Hematology Laboratory Values: Shift from Baseline to End of Reporting Period by rhHNS Dose Group– Safety Population
10.3.2.7:	Urinalysis Laboratory Values: Shift from Baseline to End of Reporting Period by rhHNS Dose Group – Safety Population
10.3.2.8:	Cerebrospinal Fluid Laboratory Values: Shift from Baseline to End of Reporting Period by rhHNS Dose Group – Safety Population
10.3.4:	Summary of Anti-rhHNS Antibody Status by rhHNS Dose Group – Safety Population

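### Laboratory and CSF change tables, shift tables and general listings cover only baseline and end of reporting period; changes in between are shown only if newly clinically significant or reported as AEs

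*SAP*

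**What the plan says.** SAP Section 5.2 lists among the primary endpoints "changes in clinical laboratory testing (serum chemistry including liver function tests, hematology, and urinalysis" and, separately, "CSF chemistries (including cell counts and inflammatory markers".

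Section 7.9.2 fixes how the laboratory endpoint is summarised. The change tables give "The observed value and change from baseline to the end of reporting period for serum chemistry, hematology and urinalysis". The shift tables give the shift with "respect to normal range between baseline and end of reporting period will also be summarized for serum chemistry, hematology, and urinalysis data". The general by-subject laboratory listings are limited to the same two time points. Section 7.9.3 carries this over to CSF: "The CSF standard chemistries will be analyzed in a manner similar to that described in Section 7.9.2". The CSF listing also holds baseline and end of period only.

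Appendix II agrees with the text. Table 10.3.2.4, for example, is titled "Cerebrospinal Fluid Values: Observed and Change from Baseline to End of Reporting Period by rhHNS Dose Group".

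For the time in between, Sections 7.9.2 and 7.9.3 plan one further kind of display: listings of "clinically significant laboratory values at any time post-baseline that were not considered clinically significant at Baseline", with the same for CSF. In Appendix IV these are listings 12.2.8.1.2, 12.2.8.2.2, 12.2.8.3.2 and 12.2.8.4.2. Section 7.9.1 (Adverse Events) separately tabulates and lists treatment-emergent AEs from the first device implantation to the end of the reporting period.

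**The concern.** The primary objective is long-term safety, and Section 4.1 puts the planned end of treatment at Month 102, although the study stopped early. Over such a period, the laboratory findings that matter most may come and go: a rise in liver enzymes after some doses, or a raised CSF cell count around a device problem. A table comparing the first value with the last cannot show these.

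The primary endpoint also gets less detail than others in the same plan. Antibody status is summarised at each assessment (Section 7.9.4). Cognitive scores, CSF heparan sulfate and MRI volumes are summarised by visit (Sections 7.6 to 7.8). Section 8, which names the data left unanalysed because of the abbreviated report, does not name laboratory or CSF data, so the restriction is not explained there.

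At stake is how the report reads. Where the tables miss an abnormality that has resolved by the end of the period, they err toward apparent safety.

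**Working it through.** No arithmetic applies beyond counting displays. The SAP states no figure on this point to reproduce.

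**Count of planned displays (Appendices II and IV)**

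- Change tables 10.3.2.1 to 10.3.2.4: 4, all baseline and end of period.
- Shift tables 10.3.2.5 to 10.3.2.8: 4, all baseline against end of period.
- Summary tables in total: 4 + 4 = 8, of which 0 use an intermediate visit or a worst value.
- Laboratory and CSF listings 12.2.8.1.1 to 12.2.8.4.2: 8. Four hold baseline and end of period only. The other four hold any post-baseline time, restricted to clinically significant values that were not so at baseline.

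**Does another section restore the missing visits?** The opening of Section 7 promises listings for every dataset it describes. Sections 7.9.2 and 7.9.3 and Appendix IV then state what the laboratory and CSF listings contain, so the general sentence does not bring intermediate visits back.

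**Where four kinds of intermediate result would appear, if the value is back at its baseline category by the end of the period**

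| Intermediate result | Change and shift tables | General listing | Any-time listing | AE displays |
|---|---|---|---|---|
| Clinically significant, not so at baseline | no | no | yes | if reported |
| Out of range, not judged clinically significant, even if repeated | no | no | no | if reported |
| Already clinically significant at baseline, then worse | no | no | no | if reported |
| Any of these reported as an AE | no | no | as above | yes |

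Rows two and three are the gap. In both, the shift table records the subject as unchanged.

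**A related consequence.** Subjects who began on 10 mg were moved to 45 mg (Section 4.3) but stay displayed under their original arm (Section 4.1). For those who switched, the one post-baseline value in these tables comes after the switch. The 10 mg column then carries no information from their time on 10 mg.

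**The case against.** The strongest reply is that transient toxicity is in fact reported. A liver enzyme rise or CSF pleocytosis judged clinically significant and new is listed by subject whenever it occurred. Anything recorded as an AE is tabulated by system organ class, preferred term and severity. The study is open-label and descriptive, has at most 12 subjects (Section 4.6), tests no hypothesis, and was closed with an abbreviated report. At that size a by-subject listing can be read in full. Nothing in Section 7.9.2 conflicts with another section.

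Most of this stands. A reader might infer that resolving toxicity is not shown at all; the four any-time listings and the AE displays rule that out. Three further inferences also go too far:

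- **Latest result.** Section 6.1 says that "the latest valid result will be selected for analysis", but only among repeated tests at one visit. It does not create the two-time-point restriction, and the SAP does not say that it removes first results from the any-time listings.
- **Assessor bias.** The SAP does not say who judges clinical significance. Open-label status alone does not establish that the judgement is biased.
- **A probability of missing an event.** The laboratory sampling schedule is not in this document, so any such figure would rest on an assumed schedule and assumed timing.

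The reply does not close the gap. AE tables show only what was reported as an AE, and the any-time listings depend on a significance judgement. Section 5.2 names laboratory and CSF results as endpoints separate from AEs, so they deserve a display that depends on neither.

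**Conclusion.** The point holds in a limited form. All 8 laboratory and CSF summary tables and 4 of the 8 listings use only the two end points. The other 4 listings are restricted to newly clinically significant values. Two classes of result therefore reach no laboratory or CSF display: intermediate out-of-range values not judged clinically significant, and intermediate worsening of values already clinically significant at baseline. They surface only if reported as AEs.

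How many results fall in these classes cannot be determined from the SAP, and no numerical size is claimed. The conclusion rests on the SAP text and the titles of its tables and listings, and assumes that the displays are produced as described. It is a cheap improvement to the reporting of a primary endpoint, below the level of an error that must be corrected before the plan can be used.

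**What to change.** 1. In shift Tables 10.3.2.5 to 10.3.2.8, add baseline to worst post-baseline value. For analytes that can be abnormal in both directions, give lowest and highest separately. Keep end of period as a second column.
2. For the worst-value derivation only, take the worst valid result within a visit, and state this as an exception to the repeat-test rule in Section 6.1.
3. List all post-baseline laboratory and CSF values outside the normal range at any visit, including those that worsen from an abnormal baseline. Keep the clinically significant flag as a column.
4. Amend Sections 7.9.2 and 7.9.3 and Appendices II and IV to match.

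No new data are needed: the any-time listings already draw on all post-baseline visits. The cost is SAP wording, reprogramming of four tables, and longer listings, which at most 12 subjects keep manageable. Some worst values will be isolated outliers, which is why the end-of-period column should stay beside them.

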7.9.3 CSF Standard Chemistries

The CSF standard chemistries will be analyzed in a manner similar to that described in Section 7.9.2.

A by-subject listing of CSF standard chemistries at baseline and the end of the reporting period will be provided. Clinically significant CSF laboratory values at any time post-baseline that were not considered clinically significant at Baseline will also be listed by subject.

7.9.4 Anti-rhHNS Antibody Assay Results

Anti-rhHNS antibodies in serum and CSF will be monitored throughout the study. Antibody status (i.e. positive or negative) at each assessment time will be summarized in terms of counts and proportion. A plot of serum antibody titer of each subject with a positive status at least one visit, over time, will be presented by dose group.

Listings of anti-rhHNS antibody results, based on serum samples and CSF samples, will be provided by subject.

7.9.5 12-lead Electrocardiogram (ECG)

The ECG data will be presented in terms of listings only.

7.9.6 Vital Signs

There are two types of vital sign assessments: IT administration and non-IT administration vital signs. Vital signs assessments will include temperature [c], pulse [bpm], blood pressure (systolic and diastolic) [mmHg], and respiration [bpm]. The non-IT administration vital signs will be measured at several times before and after the treatment start. Vital sign data will be presented as a listing only.

7.9.1 Concomitant Medications

Concomitant medications will be coded using the WHO Drug Dictionary (Version 2009, Q4 or higher).

The concomitant medications that occur from the time of surgery for IDDD implantation until the safety follow-up visit (or 30 days from the EOS visit) will be presented as a listing only.

7.9.2 IDDD Exposure and Failures

IDDD Exposure and Failures will be presented as a listing only for the subjects in the safety population with IDDD Implant.

7.10 Analysis of Pharmacokinetic Data

Pharmacokinetic assessments were not included in HGT-SAN-067, and therefore no pharmacokinetic analysis will be performed in this study.

8 CHANGES IN THE PLANNED ANALYSES

As Shire has decided to terminate this study early, and to summarize the study with an abbreviated CSR, not all data collected in this study will be analyzed, including the data for:

- Auditory Brainstem Response (ABR) (Secondary Endpoint)
- Children's Sleep Habits Rating Scale (Secondary Endpoint)
- Movement Assessment Battery for Children II (MABC-II)
- Child Health Questionnaire-50
- Child Health Questionnaire-87
- Infant Toddler QOL Questionnaire – 97 (Secondary Endpoint)
- Sanfilippo Behavior rating Scale (SBRS)
- Concomitant Therapies, and Procedures
- IDDD analysis

However, SDTM data will be available for these endpoints.

10.1 Appendix I – Calculation of DQ Scores

BSID-III: Divide the Age-equivalent score for cognitive domain (expressed in months) by the Age at Testing (expressed in months). Multiply the result by 100 to obtain percentages.

KABC-II (Age at testing 3 – 6 yrs): First calculate the average Non-verbal age equivalent score by averaging out the age-equivalent scores for the following items – Conceptual Thinking, face recognition, story completion, triangles, pattern reasoning, hand movements. Divide the average non-verbal Age-equivalent score (expressed in months) by the Age at Testing (expressed in months). Multiply the result by 100 to obtain percentages. NOTE: The average age-equivalent score (hence DQ) will be calculated based on the available items if at least two items have non-missing value.

KABC-II (Age at testing 7 – 18 yrs): First calculate the average Non-verbal age equivalent score by averaging out the age-equivalent scores for the following items – story completion, triangles, block counting, pattern reasoning, hand movements. Divide the average non-verbal Age-equivalent score (expressed in months) by the Age at Testing (expressed in months). Multiply the result by 100 to obtain percentages. NOTE: The average age-equivalent score (hence DQ) will be calculated based on the available items if at least two items have non-missing value.

10.2 Appendix II – List of Statistical Tables

Table	Table Title
10.1	Demographic and Baseline Characteristics
10.1.1:	Subject Disposition by Study and rhHNS Dose Group – Safety Population
10.1.2:	Demographics and Baseline Characteristic by rhHNS Dose Group – Safety Population
10.1.3:	Treatment Exposure by rhHNS Dose Group – Safety Population
10.2	Efficacy
10.2.1.1:	Observed Value and Change from Baseline in BSID-III Age-equivalent Scores (Months) by rhHNS Dose Group – Safety Population
10.2.1.2:	Observed Value and Change from Baseline in BSID-III DQ Scores (%) by rhHNS Dose Group – Safety Population
10.2.2.1:	Observed Value and Change from Baseline in BSID-III/KABC-II Age-equivalent Scores (Months) by rhHNS Dose Group – Safety Population
10.2.2.2:	Observed Value and Change from Baseline in BSID-III/KABC-II DQ Scores (%) by rhHNS Dose Group – Safety Population
10.2.3.1:	Observed Value and Change from Baseline in VABS-II Domains Standard Scores by rhHNS Dose Group – Safety Population
10.2.3.2:	Observed Value and Change from Baseline in VABS-II Sub-Domains Age-equivalent Scores (Months) by rhHNS Dose Group – Safety Population
10.2.3.3:	Observed Value and Change from Baseline in VABS-II Sub-Domains DQ Scores(%) by rhHNS Dose Group – Safety Population
10.2.4:	Observed Value and Change from Baseline in FPSS Domain Scores/Total Disability Scores by rhHNS Dose Group – Safety Population
10.2.5:	Observed Value and Change from Baseline in CSF Heparan Sulfate Levels by rhHNS Dose Group – Safety Population
10.2.6:	Observed Value and Change from Baseline in Brain MRI Parameters by rhHNS Dose Group – Safety Population
10.3	Safety
10.3.1.1:	Summary of Subjects with Treatment Emergent Adverse Events by rhHNS Dose Group – Safety Population
10.3.1.2:	Treatment Emergent Adverse Events by System Organ Class, Preferred Term, and rhHNS Dose Group – Safety Population
10.3.1.3:	Treatment Emergent Adverse Events by System Organ Class, Preferred Term, Severity, and rhHNS Dose Group – Safety Population
10.3.1.4:	Summary of Device Surgical Procedure Related Treatment Emergent Adverse Events by System Organ Class, Preferred Term, and rhHNS Dose Group - -Safety Population
10.3.1.5:	Summary of Device Related Treatment Emergent Adverse Events by System Organ Class, Preferred Term, and rhHNS Dose Group – Safety Population
10.3.1.6:	Summary of IT Administration Process Related Treatment Emergent Adverse Events by System Organ Class, Preferred Term, and rhHNS Dose Group- Safety Population
10.3.1.7:	Summary of Investigational Product Related Treatment Emergent Adverse Events I by System Organ Class, Preferred Term, and rhHNS Dose Group – Safety Population

Table	Table Title
10.3.1.8:	Serious Treatment Emergent Adverse Events by System Organ Class, Preferred Term, and rhHNS Dose Group– Safety Population
10.3.1.9:	Treatment Emergent Adverse Events Leading to Discontinuation by System Organ Class, Preferred Term, and rhHNS Dose Group – Safety Population
10.3.2.1:	Serum Chemistry Laboratory Values: Observed and Change from Baseline to End of Reporting Period by rhHNS Dose Group – Safety Population
10.3.2.2:	Hematology Laboratory Values: Observed and Change from Baseline to End of Reporting Period by rhHNS Dose Group – Safety Population
10.3.2.3:	Urinalysis Laboratory Values: Observed and Change from Baseline to End of Reporting Period by rhHNS Dose Group – Safety Population
10.3.2.4:	Cerebrospinal Fluid Values: Observed and Change from Baseline to End of Reporting Period by rhHNS Dose Group – Safety Population
10.3.2.5:	Serum Chemistry Laboratory Values: Shift from Baseline to End of Reporting Period by rhHNS Dose Group – Safety Population
10.3.2.6:	Hematology Laboratory Values: Shift from Baseline to End of Reporting Period by rhHNS Dose Group– Safety Population
10.3.2.7:	Urinalysis Laboratory Values: Shift from Baseline to End of Reporting Period by rhHNS Dose Group – Safety Population
10.3.2.8:	Cerebrospinal Fluid Laboratory Values: Shift from Baseline to End of Reporting Period by rhHNS Dose Group – Safety Population
10.3.4:	Summary of Anti-rhHNS Antibody Status by rhHNS Dose Group – Safety Population

10.3 Appendix III – List of Statistical Figures

Figure	Figure Title
10.2	Efficacy
10.2.1.1	Spaghetti Plot of BSID-III/KABC-II Age-equivalent Score by Chronological Age – Safety Population
10.2.1.2	Spaghetti Plot of Individual BSID-III/KABC-II DQ Score by Chronological Age – Safety Population
10.2.1.3	Mean of BSID-III/KABC-II DQ Score Over Time by rhHNS Dose Group – Safety Population Subtest: Cognitive
10.2.3.1	Spaghetti Plot of Mean Age-equivalent Score for VABS-II by Chronological Age – Safety Population
10.2.4.1	Mean of CSF Total Heparan Sulfate Over Time by rhHNS Dose Group – Safety Population
10.2.4.2	Spaghetti Plot of CSF Total Heparan Sulfate by rhHNS Dose Group – Safety Population
10.2.4.3	Spaghetti Plot of CSF Total Heparan Sulfate by Anti-rhHNS Antibody Status and rhHNS Dose Group – Safety Population: Subjects Who Ever Were Antibody Positive
10.2.5	Spaghetti Plot of Individual Brain MRI Parameters by Chronological Age – Safety Population
10.2.6	Plot of Serum Antibody Titer over Time by rhHNS Dose Group – Safety Population

10.4 Appendix IV – List of Data Listings

Listings	Data Listing Title
12.1.6	Listing of Subjects Receiving Test Drug Safety Population
12.2.1	Subject Disposition – Safety Population
12.2.2	Protocol Deviations – Safety Population
12.2.4.1	Subject Demographics – Safety Population
12.2.4.2	Medical History – Safety Population
12.2.4.3	Concomitant Medications – Safety Population
12.2.5.1	rhHNS Drug Administration – Safety Population
12.2.5.2	IDDD Exposure and Failures – Safety Population with IDDD Implant
12.2.6.1	BSID-III Data – Safety Population
12.2.6.2.1	KABC-II (3-6 years) – Safety Population
12.2.6.2.2	KABC-II (7-18 years) – Safety Population
12.2.6.3	VABS-II Data – Safety Population
12.2.6.4	FPSS – Safety Population
12.2.6.5	Heparan Sulfate Levels (CSF) – Safety Population
12.2.6.6	Urine Glycosaminoglycan (GAG) Levels- Safety Population
12.2.6.7	Brain MRI Data - Safety Population
12.2.7.1	Treatment Emergent Adverse Events - Safety Population
12.2.7.2	Serious Treatment Emergent Adverse Events - Safety Population
12.2.7.3	Listing for Treatment Emergent Adverse Events Resulting in Deaths- Safety Population
12.2.7.4	Treatment Emergent Adverse Events that Lead to Discontinuation- Safety Population
12.2.8.1.1	Hematology Laboratory Values at Baseline and End of Reporting Period by Subject and rhHNS Dose Group - Safety Population
12.2.8.1.2	Clinically Significant Hematology Laboratory Values at Any Time Post-Baseline That Were Not Clinically Significant at Baseline Post-Baseline - Safety Population
12.2.8.2.1	Serum Chemistry Laboratory Values at Baseline and End of Reporting Period by Subject and rhHNS Dose Group - Safety Population
12.2.8.2.2	Clinically Significant Serum Chemistry Laboratory Values at Any Time Post-Baseline

Listings	Data Listing Title
	That Were Not Clinically Significant at Baseline - Safety Population
12.2.8.3.1	Urinalysis Laboratory Values at Baseline and End of Reporting Period by Subject and rhHNS Dose Group - Safety Population
12.2.8.3.2	Clinically Significant Urinalysis Laboratory Values at Any Time Post-Baseline That Were Not Clinically Significant at Baseline - Safety Population
12.2.8.4.1	Cerebrospinal Fluid Values at Baseline and End of Reporting Period by Subject and rhHNS Dose Group - Safety Population
12.2.8.4.2	Clinically Significant CSF Laboratory Values at Any Time Post-Baseline That Were Not Clinically Significant at Baseline Post-baseline - Safety Population
12.2.8.5	Vital Signs - Safety Population
